12.2 Procedures to Support Parents/Guardians and Maintain Participant Safety

In this trial, normal pathways of care will be encouraged. However, there is a responsibility to balance this approach with the need to ensure the safety of all participants, particularly those treated with oral antibiotics who have been discharged prior to the urine culture results. In addition to standard clinical practice, additional measures for trial participants who have been randomised to oral antibiotics will be:

- Parents/guardians will be provided with a dedicated telephone contact number, allowing direct access to the local clinical team between 8am – 8pm Monday to Friday, should they have any questions or concerns.
- Parents/guardians will be provided with a telephone contact number for the paediatric emergency department at the local site, which can be used at all other times, should they have any questions or concerns.
- Parents/guardians will be reassured that they can attend the emergency department at any time, should they have any concerns.
- Follow up assessments will be performed by an appropriately trained member of the clinical team via telephone at 24 hours and 36-48 hours after randomisation, asking the parent/guardian to report if their child has ongoing fever or other symptoms of concern. Symptom data will be monitored remotely during trial follow up by the local clinical team. If there are any concerns parents/guardians will be advised to attend the emergency department so that a medical review can be undertaken.

12.3 Participant Follow-Up at Day 7 and Day 28

Follow up assessments will be performed via telephone at day 7 (+/- 1 day) and day 28 (+/- 3 days). This will include an ongoing review of symptoms, antibiotic administration and adverse events. In addition, site staff should remind parents/guardians to complete the PedsQL Infant Questionnaire (day 7 and day 28) and the PedsQL Family Impact Questionnaire (day 7). At day 28, site staff should also administer the Health Resource Use and Activities Questionnaire via telephone.

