7 TRIAL SETTING AND PARTICIPANT ELIGIBILITY CRITERIA

7.1 Trial Setting

Recruitment for the trial will take place in at least 18 paediatric emergency departments (EDs) and assessment units from across the UK, from within the Paediatric Research in the UK and Ireland (PERUKI) research network and the General and Adolescent Paediatric Research in the United Kingdom & Ireland (GAPRUKI) research network. Sites will be selected based on a wide geographical spread and they must provide evidence that they have:

- Access to the target population
- Local PI willing to lead the trial at that site and a local trial team
- A proven track record of participating in research
- Availability of either point-of-care urinalysis or laboratory microscopy 24 hours a day
- Access to laboratory testing for full blood count, C-reactive protein, creatinine 24 hours a day
- Ability to dispense trial medications 24 hours a day
- Ability to provide a dedicated phone number that can be accessed by parents/guardians between 8am and 8pm 7 days a week
- Ability to provide a departmental phone number that can be accessed by parents/guardians outside of these times

Staff must also comply with the protocol, standard operating procedures (SOPs), the principles of Good Clinical Practice (GCP), regulatory requirements, and be prepared to participate in appropriate trial training. Training will be provided to sites who participate in the study. A list of study sites will be maintained in the TMF.

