10.1 Primary Outcome

The primary outcome is treatment failure (i.e. additional parenteral antibiotics) within seven days of randomisation.

Additional parenteral antibiotics in the standard care group is defined as:

- (i) administration of an additional parenteral antibiotic not prescribed as part of initial empirical treatment
- (ii) a change of parenteral antibiotics from standard empirical treatment
- (iii) re-commencing parenteral antibiotics after the decision to terminate parenteral antibiotics.

For the intervention group additional parenteral antibiotics are defined as administering parenteral antibiotics for any reason.

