12.1 Participant Assessments

The frequency of assessments and follow up are detailed in the schedule of assessments (Table 6). The schedule defines the timing of assessments (with windows) necessary for data collection. Participants should be followed until the final follow-up assessment at day 28, even if antibiotics have been discontinued.

The decision to discharge a participant home is not mandated by the allocation to the oral antibiotic treatment group. The local clinical team should determine when the participant should be discharged and have agreed that it is an appropriate management strategy.

Table 6: Schedule of Assessments

Day/Timepoint	Screening (Day 0)	Baseline (Day 0)	Within 24* Hours of Randomisation	36 – 48* Hours After Randomisation	Follow Up Day 7# (+/- 1 day)	Follow Up Day 28# (+/- 3 days)
At Hospital/Remote	Hospital	Hospital	Hospital/Remote	Hospital/Remote	Remote	Remote
Point of Care Dipstick Urinalysis	x					
Urine sample sent for microscopy and culture	x					
Eligibility	x					
Consent (Trial)		x				
Admission Details		x				
Demographics		x				
Medical History		x				
Symptoms		x	x	x	x	x
Physical Examination		x				
Full Blood Count (including CRP, Creatinine, Electrolytes)		x				
Medications		x	x	x	x	x
Hospital Resource Use			x	x	x	x
Antibiotic Administration (pre randomisation)		x				
Randomisation		x				
Antibiotic Administration (post randomisation) Including Adherence/Tolerability			x	x	x	x
Urine Culture Results			x	x		
Escalation in the level of care/Readmission			x	x	x	x
Adverse Events/ Serious Adverse Events		x	x	x	x	x
[§] PedsQL Infant (completed by parent/guardian)			x		x	x
[§] PedsQL Family Impact (completed by parent/guardian)					x	
SWAT Questionnaire on Consent (completed by parent/guardian)				x		
Health Resource Use and Activities Questionnaire (administered by site staff via telephone)						x

*Assessments will be face-to-face (hospital) or may be by telephone (remote) for participants who have been discharged. Within 24 hours, the parent/guardian should complete the PedsQL Infant Questionnaire. Within 36-48 hours, site staff should remind the parent/guardian to complete the SWAT Questionnaire.

#Assessments will be by telephone (remote) for both cohorts.

At day 7, site staff should remind the parent/guardian to complete the PedsQL Family Impact Questionnaire.

At day 7 and day 28, site staff should remind the parent/guardian to complete the PedsQL Infant Questionnaire.

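### Section 12.2, Table 6 and section 7.1 conflict on which arm gets early support and contact, when the first contact falls, and which days the phone line is open; following 12.2 would make post-discharge prompting differ by arm.

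*Protocol*

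**What the plan says.** Three places in the protocol govern early contact with families.

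- **Section 12.2** begins from the safety of all participants, with particular concern for infants on oral treatment who go home before culture results. It then lists "additional measures for trial participants who have been randomised to oral antibiotics will be": a dedicated line "allowing direct access to the local clinical team between 8am – 8pm Monday to Friday", an emergency department number at other times, reassurance about attending at any time, and assessments by the clinical team "via telephone at 24 hours and 36-48 hours after randomisation". The last item includes remote symptom monitoring and advice to attend if there are concerns.
- **Section 12.1, Table 6** has columns headed "Within 24* Hours of Randomisation" and 36-48 hours after randomisation, with no arm named. Its footnote reads "Assessments will be face-to-face (hospital) or may be by telephone (remote) for participants who have been discharged". Both columns collect symptoms, antibiotic administration, escalation or readmission, and adverse events.
- **Section 7.1** makes it a condition of site selection that the site can offer a "dedicated phone number that can be accessed by parents/guardians between 8am and 8pm 7 days a week", plus a departmental number at other hours. No arm is named.

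Two further places explain why this matters. Section 8.2.4 leaves parents, clinicians and outcome assessors unblinded. Section 10.1 states that in the intervention group "additional parenteral antibiotics are defined as administering parenteral antibiotics for any reason".

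**The concern.** A site cannot tell from the protocol whether a comparator infant who has gone home is to have the line, the clinician-led calls and the advice to attend. Nor can it tell whether the first contact belongs at hour 24 or anywhere before it, or whether the line must be staffed at weekends.

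Under 12.2 as worded, oral-arm families have an easier route to the clinical team and are prompted to come back, while discharged comparator families are not given that support as a trial measure. A prompted visit can feed several outcomes: parenteral treatment (primary outcome), admission from home (a component of escalation in care, section 10.2) and adverse events that parents report unprompted (section 16.2). Part of any difference between arms could then reflect contact intensity and not the route of the antibiotic.

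**Working it through.** **1. The passages side by side.**

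| Point | Section 12.2 | Table 6 | Section 7.1 |
|---|---|---|---|
| Who | oral arm | all participants; telephone if discharged | parents in general |
| First contact | at 24 hours | any time within 24 hours | not addressed |
| Second contact | 36-48 hours | 36-48 hours | not addressed |
| Days of line, 8am-8pm | Monday to Friday | not addressed | seven days a week |

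The conflict on days (12.2 against 7.1) and on the first contact (12.2 against Table 6) is direct. On arm, 12.2 is narrower than Table 6 for the calls, and narrower than 7.1 for the line.

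**2. What is already the same in both arms.** Table 6 and section 16.2 put the same scheduled questions on symptoms, antibiotics, escalation and adverse events to everyone, and the day 7 and day 28 calls (section 12.3) are by telephone in both arms. If Table 6 governs the scheduled contacts, the difference by arm is confined to unscheduled contact (the line), remote monitoring and advice to attend.

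**3. The plan's own figure.** Inputs from section 14.1: failure 0.5% (taken as equal in both arms), margin 2%, one-sided 0.025, power 90%; 1:1 allocation from section 8.2.1.

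n per arm = (1.960 + 1.282)² × 2 × 0.005 × 0.995 / 0.02² = 10.507 × 0.00995 / 0.0004 = 261.4, so 262 per arm and 524 in total. With 10% loss, 262/0.9 rounds up to 292 per arm, 584 in total. Both figures match.

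**4. Sensitivity to one or two events.** Expected failures per arm: 0.005 × 262 = 1.3. One extra failure moves the risk difference by 1/262 = 0.38 points, about a fifth of the margin.

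Upper limits at 262 per arm (oral vs control failures). Wald is d + 1.96 × √[p₁(1−p₁)/262 + p₂(1−p₂)/262]; the score limit is Miettinen-Nurminen.

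| Failures | Wald | Score |
|---|---|---|
| 1 vs 1 | 1.06% | 1.78% |
| 2 vs 1 | 1.67% | 2.40% |
| 3 vs 1 | 2.25% | 2.98% |

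For 2 vs 1 by Wald: d = 0.382 points, SE = 0.659 points, and 0.382 + 1.96 × 0.659 = 1.67. Starting from 1 vs 1, one extra oral-arm failure crosses 2% under the score limit and two cross it under Wald. Section 14.2.2 specifies a generalised linear model for the risk difference and does not name the interval, so both are shown.

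**5. Cost in power, under an assumption.** The protocol gives no rate of contact-prompted failure, so the excess e in the oral arm is assumed. Power = Φ[(0.02 − e)/SE − 1.96], with control failure at 0.5%.

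| Assumed excess (points) | Extra infants of 262 | Power, normal | Power, binomial enumeration with Wald limit |
|---|---|---|---|
| 0 | 0 | 90% | 87% |
| 0.25 | 0.7 | 72% | 71% |
| 0.5 | 1.3 | 51% | 55% |
| 1.0 | 2.6 | 21% | 28% |
| 1.5 | 3.9 | 7% | 12% |

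**The case against.** The strongest reply is that 12.2 gives a safety reason. Oral-arm infants may leave before culture results, while comparator infants continue parenteral treatment until then (typically 36-48 hours, section 8.1) and many will probably be under direct observation. Extra safety-netting for earlier discharge can be seen as part of the strategy in a pragmatic open-label trial. This stands as a reason for the measures. It does not settle which passage a site should follow, nor does it cover the rest of the seven-day window once comparator infants are also at home.

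Three stronger readings are tempting and are not supported.

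- *That failure and adverse events are in fact sought harder in the oral arm.* Table 6 and sections 12.3 and 16.2 set the same scheduled questions for everyone. The imbalance arises only to the extent that sites follow 12.2, and then mainly through unscheduled contact after discharge.
- *That discharged comparator infants have no line or monitoring.* Section 7.1 requires the line without an arm limit, Table 6 keeps the 36-48 hour and day 7 contacts for all, and 12.2 describes its measures as additional to standard practice.
- *That a single extra failure overturns the result.* With 1 vs 0 failures the score limit is 2.13% but Wald gives 1.13%. Under the score limit even 2 vs 2 gives 2.06%, so much of the fragility comes from few events and the choice of interval, not from the contacts.

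A gap of 35-47 hours between planned contacts can also be built from Table 6, but only by assuming both contact and discharge at hour 1, which the protocol does not describe.

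**Conclusion.** The inconsistency is established on three points: arm, timing of the first contact, and days of the line. The bias is a risk and not a demonstrated effect. It depends on sites following 12.2 over Table 6 and 7.1, it is clearest after discharge, and its size cannot be taken from the documents.

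On the primary outcome the direction is conservative: extra detection in the oral arm costs power and could make non-inferiority fail, but would not produce a false claim of it. Escalation in care and spontaneously reported adverse events could also look worse in the oral arm for the same reason. With 1.3 failures expected per arm, one or two prompted events are enough to matter, whether one or two depending on the interval used. The planned 524 and 584 are unaffected. This should be corrected, with medium confidence in its practical effect.

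**What to change.** 1. Reconcile section 12.2, Table 6 and section 7.1 on which arm or arms receive the line, the calls and the advice, on the timing of the first contact, and on the days the line is open.
2. State that scheduled contacts used to ascertain outcomes have the same timing and symptom questions in both arms and are triggered by discharge status, as the Table 6 footnote already implies.
3. If any support is deliberately kept for one arm, add a CRF field recording whether a trial contact prompted each re-attendance, so that its effect on the outcomes can be shown. This has to be collected during conduct; an analysis plan cannot recover it later.

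The clinical content of the contacts, and which support rule applies, are for the sponsor to decide. The cost is protocol and site-guide wording, one CRF field and possibly a few more calls from comparator families. The sample size does not change.

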12.4 Study Instruments for Participant Follow-Up

12.4.1 Paediatric Quality of Life (PedsQL) Infant Scales 1-12 month Version (Acute).

The PedsQL Infant Scales [32] 1-12 month Version is a 36-item modular, parent/guardian reported, health-related quality of life (HRQOL) instrument encompassing 5 scales: Physical Functioning (6 items), Physical Symptoms (10 items), Emotional Functioning (12 items), Social Functioning (4 items) and Cognitive Functioning (4 items). The Acute version asks the parent/guardian how much of a problem each item has been during the past 7 days. Responses are measured on a 5-point Likert scale (0 = never a problem; 1 = almost never a problem; 2 = sometimes a problem; 3 = often a problem; 4 = almost always a problem). Items are reverse scored and linearly transformed to a 0–100 scale (0 = 100, 1 = 75, 2 = 50, 3 = 25, 4 = 0), so that higher scores indicate better HRQOL. The total score is calculated as the sum of all the items divided by the number of items answered. Scale scores are computed as the sum of the items divided by the number of items answered. The PedsQL has previously been shown to be a valid and responsive indicator of HRQOL for short-term febrile illnesses evaluated in the ED [33].

12.4.2 Paediatric Quality of Life (PedsQL) Family Impact Module (Acute)

The PedsQL Family Impact Module [34] is 36-item modular parent/guardian self-reported, HRQOL instrument encompassing 6 scales: Physical Functioning (6 items), Emotional Functioning (5 items), Social Functioning (4 items), Cognitive Functioning (5 items), Communication (3 items), Worry (5 items), and 2 scales measuring parent/guardian reported family functioning: Daily Activities (3 items) and Family Relationships (5 items). The Acute version asks the parent/guardian how much of a problem each item has been during the past 7 days. Responses are measured on a 5-point Likert scale (0 = never a problem; 1 = almost never a problem; 2 = sometimes a problem; 3 = often a problem; 4 = almost always a problem). Items are reverse scored and linearly transformed to a 0–100 scale (0 = 100, 1 = 75, 2 = 50, 3 = 25, 4 = 0), so that higher scores indicate better HRQOL. The total score is calculated as the sum of all the items divided by the number of items answered. Scale scores are calculated as the sum of the items divided by the number of items answered. Parent/guardian HRQOL Summary Score (20 items) is calculated as the sum of the items divided by the number of items answered in the Physical, Emotional, Social, and Cognitive Functioning Scales. The Family Functioning Summary Score (8 items) is computed as the sum of the items divided by the number of items answered in the Daily Activities and Family Relationships Scales. Only one parent/ guardian needs to complete the instrument and their relationship to the child will be recorded.

12.4.3 Health Service Use and Activities Impact Questionnaire

A study specific questionnaire will measure participants' use of primary care services since discharge as well as the impact of the participants' health condition on the parents'/guardians' ability to work and undertake their usual activities.

13 DATA COLLECTION and MANAGEMENT

13.1 Data Collection

To ensure accurate, complete, and reliable data are collected, the CTU will provide training to site staff. All data for an individual participant will be collected and recorded in source documents and transferred onto a bespoke, web-based, electronic CRF for the study. A data dictionary, record of automatic and manual data queries, and a full audit trail, will ensure data captured are consistent, reliable, and fully compliant with GCP and any other relevant regulatory requirements. For routinely collected clinical data the NHS record will be the source document. Participant identification on the CRF will be through their unique participant study number, allocated at the time of randomisation. Data will be collected and recorded on the electronic CRF by the PI or designee as per the CRF submission guidelines.

For the economic evaluation paediatric HRQoL will be measured using the PedsQL administered within 24 hours of randomisation, 7 days and 28 days. Hospital resource use data including readmissions and outpatient attendance will be collected via the CRF and primary care use will be collected using a brief questionnaire administered by site staff via telephone at 28 days. The questionnaire will also measure the impact of the participants' health condition on the parents'/guardians' ability to work or perform usual activities (see section 14.3). The PI or designee will provide the parent/guardian with the questionnaires prior to discharge. As part of the telephone follow up at 7 days and 28 days, the site staff will remind the parent/guardian to complete the questionnaires and return these in prepaid envelopes provided to the Trial Co-ordinating Centre.

13.2 Data Quality

The CTU will provide training to site staff on trial processes and procedures including CRF completion and data collection. Source data verification (SDV) will be completed by the CTU and will check the accuracy of entries on the electronic CRF against the source documents and adherence to the protocol. The extent of SDV to be completed is detailed in the Monitoring Plan.

Quality control is implemented by the CTU in the form of Standard Operating Procedures (SOPs), which encompass aspects of the clinical data management process, and ensure standardisation and adherence to International Conference of Harmonisation Good Clinical Practice (ICH GCP) guidelines and regulatory requirements.

Data validation will be implemented and discrepancy reports will be generated following data entry to identify discrepancies such as out of range, inconsistencies or protocol deviations based on data validation checks programmed in the clinical trial database.

A DMEC will be convened for the study to carry out reviews of the study data at staged intervals during the study.

13.3 Data Management

Following the entry of participant data into the study database, the data will be processed as per the CTU SOPs and the study specific Data Management Plan (DMP). Data queries will be generated electronically for site staff to clarify data or provide missing information, with the expectations that these queries will be completed within 14 days of receipt. All queries will be responded and amended within the study database.

14 STATISTICAL CONSIDERATIONS

14.1 Sample Size

With a treatment failure rate (i.e. additional parenteral antibiotics within 7 days of randomisation) of 0.5% and a non-inferiority margin of 2%, 524 participants are required based on 90% power and a 1-sided 97.5% Confidence Interval. Of the required population, it is estimated that up to 10% might not provide 7-day follow up. Therefore, a sample size of 584 is needed to obtain the 524 required for analysis.

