4.2 Rationale for the Study

In the UK, the diagnosis and management of febrile young infants is primarily guided by the National Institute for Health and Care Excellence (NICE). Clinical guidelines CG54, NG143 and NG111 recommend that all febrile infants, 90 days and younger, with a suspected UTI are admitted to hospital and treated with parenteral antibiotics [13-15]. However, this guidance is not always followed. In preparation for this project, we conducted the Febrile Infants Diagnostic assessment and Outcome study (FIDO) study [1] as an observational cohort study in six Paediatric Emergency Research in the UK and Ireland (PERUKI) sites between 31 August 2018 and 01 September 2019 [1]. The aims were to report the aetiology of infections amongst young febrile infants, validate clinical practice guidelines and assess current UK practices. That pilot work demonstrated that the average Paediatric Emergency Department in the UK and Ireland sees approximately one infant per day with a history of fever (based on 1942 cases). Of those with fever on arrival to hospital (n=555), 500 (90%) were admitted to hospital and 423 (76%) received parenteral antibiotics [1]. However, of these 555 infants febrile on arrival to hospital, only 11 (2%) had bacterial meningitis or bacterial sepsis and (67) 12% had a UTI [1].

Of the 555 febrile infants in the study, 114 (21%) met the American Academy of Paediatrics definition of “low risk” [>28 days of age, appear well, CRP of <20mg/l, absolute neutrophil count (ANC) < 5,200/mm³] and had abnormal urinalysis [2]. According to NICE guidance, all these infants should have been admitted to hospital and been given parenteral antibiotics [13-15] but only 81 (71% of the 114) were admitted to hospital and 33 (29%) were discharged home from ED with no oral antibiotic therapy. Amongst these 114 lower risk infants, 4 (4%) were diagnosed with a confirmed UTI and there were no cases of meningitis or bacterial sepsis. There was one case of treatment failure occurring in an infant who was not given parenteral antibiotics.

This pilot work demonstrates that clinicians do not routinely follow NICE guidance and that there appears to be considerable uncertainty regarding the management of well appearing febrile infants with abnormal urinalysis.

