14.2 Data Analysis

14.2.1 Analysis Population

Primary analysis will be conducted on all outcome data obtained from all participants as randomised and regardless of protocol adherence, i.e. intention to treat (ITT) analysis. Per-protocol analysis will also be conducted which will involve a comparison of treatment groups that includes only those participants who completed the treatment originally allocated. In view of the risk of bias arising from either analysis alone in a non-inferiority trial, we will conclude that non-inferiority of the intervention has been proven only if it is demonstrated in both analyses.

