14.2.2 Statistical Methods

Baseline characteristics, follow-up measurements and safety data will be described using appropriate descriptive summary measures depending on the scale of measurement and distribution.

Analyses for the primary outcome will be 1-sided and at a significance level of 0.025 and investigated using generalised linear models (GLM) to estimate the risk difference (RD). The difference in treatment failure rate (95% CI) will be compared to the non-inferiority margin of 2%. Non-inferiority is established by showing that the upper bound of a one-sided 97.5% confidence interval for the difference in treatment failure rate is <2%.

A secondary comparison of the primary outcome between the two groups will be investigated using GLM, adjusting for site, sex, age, antibiotic use and other covariates

All remaining analyses for secondary outcomes will be two-sided and at a significance level of 0.05.

Binary outcomes between the two groups will be investigated using GLM, adjusting for covariates.

Comparison of continuous outcomes between the two groups will be investigated using independent t-tests or ANCOVA if appropriate or nonparametric equivalents.

We will include sensitivity analyses looking at treatment failure (day 28) and escalation in care (day 7 and day 28) for those children with a confirmed UTI*.

Statistical diagnostic methods will be used to check for violations of the assumptions, and transformations will be performed where required.

A detailed statistical analysis plan (SAP) will be written by the trial statistician prior to the final analysis.

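### Section 14.1's 90% power and the one-sided 0.025 error level are not jointly met with 524 infants, because the normal formula fails at about 1.3 expected failures per arm

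*Protocol*

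**What the plan says.** Section 14.1 sets the assumptions: "With a treatment failure rate (i.e. additional parenteral antibiotics within 7 days of randomisation) of 0.5% and a non-inferiority margin of 2" per cent. It concludes that "524 participants are required based on 90% power and a 1-sided 97.5% Confidence Interval", and allows for up to 10% without 7-day follow-up, giving 584 randomised. Allocation is 1:1 (section 8.2.1), so 262 per arm are analysed.

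Section 14.2.2 fixes the test: "Analyses for the primary outcome will be 1-sided and at a significance level of 0.025", using a generalised linear model for the risk difference. Non-inferiority is shown if the "upper bound of a one-sided 97.5% confidence interval for the difference in treatment failure rate is <2" per cent. The type of interval is not named. Section 14.2.1 adds that "we will conclude that non-inferiority of the intervention has been proven only if it is demonstrated in both analyses".

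Section 14.1 gives no source for the 0.5%. The only treatment-failure count in the protocol is in section 4.2, among 114 low-risk infants in the earlier cohort: "There was one case of treatment failure occurring in an infant who was not given parenteral antibiotics".

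**The concern.** The sample-size formula treats the difference between two observed proportions as normally distributed with a known standard error. At 0.5% and 262 per arm, the expected count is 262 × 0.005 = 1.3 failures per arm. The chance of no failures is 0.995^262 = 27% in a given arm and 7% in both. The decision then turns on one or two infants, and the choice of interval decides how many oral-arm failures are tolerated.

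If power is really well below 90%, a truly equivalent oral strategy has a larger chance of missing non-inferiority than the plan states, and a missed result could be misread as evidence against oral treatment. If power is kept near 90% by using a plain Wald interval, the chance of wrongly declaring non-inferiority exceeds the 2.5% that section 14.2.2 promises.

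**Working it through.** **Inputs.** Failure rate 0.5% in both arms, margin 0.02, one-sided 0.025, 90% power, 10% loss (section 14.1); success if the upper bound is below 2% (section 14.2.2); 1:1 allocation (section 8.2.1).

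**1. Reproducing the plan.** Unpooled normal formula:

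n per arm = (1.960 + 1.2816)² × 2 × 0.005 × 0.995 / 0.02² = 261.4, rounded up to 262, or 524 in total.

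Normal-theory power at 262: standard error = √(2 × 0.005 × 0.995 / 262) = 0.00616; 0.02/0.00616 − 1.960 = 1.285; power 90.1%. Loss: 262/0.9 = 291.1, so 292 per arm, or 584. The plan's figures reproduce.

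**2. The decision rule in events.** The largest number of oral failures (of 262) that still gives an upper bound below 2%, by number of parenteral failures:

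| Parenteral failures | 0 | 1 | 2 | 3 | 4 |
|---|---|---|---|---|---|
| Wald | 2 | 2 | 2 | 3 | 3 |
| Agresti-Caffo, profile likelihood | 1 | 1 | 2 | 2 | 3 |
| Score | 0 | 1 | 1 | 2 | 3 |

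**3. Exact power at 0.5% in both arms.** The binomial probabilities of 0 to 5 failures in 262 are 0.269, 0.354, 0.232, 0.101, 0.033 and 0.009. The cumulative probabilities of at most 0, 1, 2 and 3 are 0.269, 0.623, 0.855 and 0.956. Power is the sum, over parenteral counts, of the probability of that count times the probability that oral failures stay within the limit. The first terms are:

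- Wald: 0.269×0.855 + 0.354×0.855 + 0.232×0.855 + 0.101×0.956 + …
- Agresti-Caffo: 0.269×0.623 + 0.354×0.623 + 0.232×0.855 + 0.101×0.855 + …
- Score: 0.269×0.269 + 0.354×0.623 + 0.232×0.623 + 0.101×0.855 + …

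**4. Exact one-sided error.** The same sum with the oral rate 2 points above control.

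| Interval (262 per arm) | Power at 0.5% v 0.5% | Error at control 0.5%, oral 2.5% | Worst-case error |
|---|---|---|---|
| Wald | 87.0% | 5.1% | about 10% |
| Agresti-Caffo, profile likelihood | 71.5% | about 2.5% | 3.2% |
| Score | 56.6% | 1.5% | 2.3–2.4% |

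For the first two rows the worst case is a control rate near 0. There the error is the chance of at most 2 oral failures (10.3%) or at most 1 (3.2%) when the oral rate is 2%. The Wald power counts 0 v 0 as a success, although that interval has no width; without it, power is 87.0 − 7.2 = 79.8%.

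**5. If nobody is lost (292 per arm).** Power is 87% (Wald), 78% (Agresti-Caffo or profile likelihood) and 69% (score).

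**6. Sensitivity at 262 per arm.**

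| Oral v parenteral rate | Plan's formula | Wald | Agresti-Caffo | Score |
|---|---|---|---|---|
| 0.5% v 0.5% | 90% | 87% | 72% | 57% |
| 0.88% v 0.88% | 69% | 69% | 55% | 46% |
| 1.0% v 1.0% | 63% | 64% | 51% | 44% |
| 1.0% v 0.5% | 51% | 55% | 37% | 26% |

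The 0.88% is 1/114 from section 4.2, with an exact 95% interval of 0.02% to 4.8%.

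**The case against.** The arithmetic is not at fault: 524, 90% and 584 all follow from the stated inputs by a standard formula. That stands; the fault is relying on the approximation at these event counts.

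The interval type is ordinary content for a statistical analysis plan, and the formula in section 14.1 corresponds to a Wald interval, whose exact power of 87% is only three points short. It is fair that the missing interval is not itself an error. But the protocol also fixes the 0.025 level, and the Wald interval roughly doubles it at the design rate. Choosing the interval elsewhere does not reconcile power, error and sample size as stated here.

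A reader might infer that the true power is 57%. That goes too far. It belongs to the score interval, which spends only 1.5% error at the design rate; about 72% is the fair figure for an interval close to 2.5% there. Loss is also given as up to 10%, so 262 per arm is the low end.

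A reader might also infer that the earlier cohort shows 0.5% to be wrong and power to be 69%. The protocol does not support that. The rate rests on one event, and at a true 0.5% the chance of at least one failure in 114 is 1 − 0.995^114 = 44%. The failure was in an infant not given parenteral antibiotics, and 33 of the 114 went home without oral antibiotics. That group was defined with CRP and neutrophil limits which sections 7.3.1 and 7.3.2 do not apply, and the trial's own oral-arm rule is broad (section 10.1: "For the intervention group additional parenteral antibiotics are defined as administering parenteral antibiotics for any reason"). The 0.88% is useful only as a sensitivity assumption.

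**Conclusion.** The point holds. Under the plan's own assumptions, with 262 analysed per arm and no true difference, none of the intervals examined gives both 90% power and 2.5% one-sided error. With error near or below 2.5% at the design rate, power is about 72% (Agresti-Caffo or profile likelihood) or 57% (score). Wald reaches 87% with about 5% error. Analysing all 584 does not close the gap.

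It would be too strong to say that failing to show non-inferiority is the likely result. If both true rates are 0.5%, the chance of failing is 28% to 43% with the error-controlling intervals (100 − 71.5 and 100 − 56.6) and 13% with Wald, against the 10% stated. It reaches half or more only under less favourable assumptions, such as score at 0.88%.

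These figures are for one unadjusted analysis. Requiring success in both the intention-to-treat and per-protocol analyses can only lower them; by how much cannot be computed from the protocol.

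**What to change.** Keep the sample size at 584 and make these changes:

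- In sections 14.1 and 14.2.2, name an interval for the primary risk difference that holds close to 2.5% one-sided error with sparse events, and say how it is obtained when an arm has no failures.
- Replace the 90% with the exact power of that interval at 262 per arm: about 72% for Agresti-Caffo or profile likelihood, about 57% for score. Report its exact one-sided error beside it.
- Add a short table like the one in step 6, covering 0.5%, 0.88% and 1.0% in both arms and 1.0% oral v 0.5% parenteral. Label the higher rates as assumptions, and give the 0.02% to 4.8% interval around 1/114.
- State that the power is for a single analysis and that the joint intention-to-treat and per-protocol requirement can only lower it.

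The cost is a rewritten paragraph and a less favourable stated power, with no extra patients. For scale, a true 90% at 0.5% would need about 740 analysed with Agresti-Caffo or about 900 with score; this point does not ask for that.
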